The proposed project is based on the premise that the annual Medicare enrollment period in an institutional context presents an ideal opportunity to reach eligible, high-risk elders. Retired adults, considering their future health care coverage needs, may be particularly receptive to the proposed intervention and employers and insurers providing such benefits may be more likely to offer programs that have been demonstrated to be effective and sustainable. Thus, we propose to implement the GLB 12-session intervention (GLB-12) as part of the annual health benefit package offered to high-risk retirees at a large public university. Participants will be 320 non-diabetic adults, aged 65-80, with a BMI \geq 27 and at least one additional cardio-metabolic risk factor. First, we will evaluate the feasibility of recruiting for and implementing an in-person group program (GLB-12) within this infrastructure. Next, we will conduct a randomized, controlled comparison of two follow up protocols for the remainder of one year of intervention, 8-sessions of continued small group contact by telephone (GLB+8TC; N = 160) or a 2-newsletter control condition (GLB + NC; N = 160). The primary aims are to:

Aim 1: Document that the GLB-12 intervention is feasible and effective when implemented with Medicare enrolled retirees.

Hypothesis 1 (feasibility): We will enroll 107 participants per year, they will complete 65% of sessions, return 50% of self-monitoring records and report above average program satisfaction at the month 4.

Hypothesis 2 (effectiveness): Participants will achieve 5% weight loss and 150 minutes of self reported physical activity per week, and show corresponding waist, glucose, blood pressure and lipid improvements (adjusted for medication use) at month 4.

Aim 2: Evaluate the effects of continued small group contact by telephone (GLB+8TC) compared to a newsletter control condition (GLB+NC) on anthropometric, cardio-metabolic, physical function and health related quality of life (HRQL) measures at 12- and 24-months follow up.

Hypothesis 3: GLB+8TC will be associated with more favorable weight, waist, glucose, lipid, blood pressure gait speed, grip strength, balance and HRQL at month 12 and 24 assessments.

An exploratory aim will be to evaluate direct program costs and self reported health care utilization.

1.3**Background: Briefly describe previous findings or observations that provide the background leading to this proposal.**

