The current research can be classified as a feasibility/effectiveness design . First we will document the feasibility of community based implementation of an evidence-based 12-session Group Lifestyle Balance (GLB-12) intervention among retirees and/or their dependent spouses/partners who have enrolled or are about to enroll in Medicare benefits through the University of Pittsburgh. We will also recruit from other community locations. Following implementation of the non-randomized GLB-12, participants will be assigned by a stratified block randomization scheme to continued telephone contact (GLB + 8TC; N = 160) or to newsletter control (GLB + NC; N = 160) for the remainder of the one year intervention. Stratification will be based on the category of percent weight loss achieved during the first phase of intervention (<3.5 % and >3.5%). Major outcome assessments will be conducted at 0, 4, 12 and 24 months.

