- **duration of procedures**
- **timeline of study procedures**

Study Timeline

There will be at least three annual waves of recruitment. Baseline and annual assessments will be conducted in the period between January and March of each year; additional recruitment may occur between May and July of each year. Waves of intervention will commence within 8-12 weeks of screening and enrollment. Prior experience in our community based GLB projects indicates that these are optimal times to initiate programs. It will also allow for some groups to start in early Spring to accommodate older adults who travel during the winter months. If recruitment targets are lagging, there may be an additional wave of recruitment and intervention commencing in May/June annually---all procedures will be identical.

Training and Supervision.

The GLB-12 intervention will be administered in groups of approximately 15-20 participants

by three part-time lifestyle coaches, with Bachelor's degree training at minimum, and previous experience in health promotion, health education or lifestyle interventions. They will be trained by the Diabetes Prevention Support Center staff in a two-day workshop conducted by a nurse diabetes educator (CDE), registered dietitian, exercise specialist and a behavioral scientist. These individuals will be available for specialty consultation as needed. Each coach will conduct 3-10 groups (GLB-12) per year and be responsible for all associated follow up protocols. Drs. [name] and [name] will provide additional monitoring and supervision for the telephonic continued contact coaching protocol and each lifestyle coach will be required to audiotape 10% of their telephone contact sessions. Independent reviewers will complete a session content checklist of these recordings as an intervention fidelity check. If necessary, lifestyle coaches will be trained at remote campus locations to implement the GLB-12.

Description of GLB-12 session intervention.

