Analysis Plan: The overall approach will be to report descriptive statistics, including the total number of participants enrolled, the distribution of the number of GLB-12 sessions completed, the percentage of participants completing 8 (65%) or more sessions (the definition for acceptable attendance), the percentage of participants who return six (50%) or more of the self monitoring records (the definition for acceptable behavioral adherence) and the distribution of program satisfaction ratings. Summary descriptive statistics will include mean, median, standard deviation and confidence intervals for continuous variables and proportions, ranges and percentiles for categorical variables.

Hypothesis 2 (effectiveness): On average, participants will achieve $\geq 5\%$ weight loss (the definition of acceptable weight outcome in prevention programs) and ≥ 150 minutes of self reported moderately vigorous physical activity minutes per week (the recommended level in prevention programs), and show corresponding waist, glucose, blood pressure and lipid improvements (adjusted for medication use).

Analysis Plan: For the weight measure, we will examine both absolute weight change (kg) and percent weight change pre to post-intervention (0-4 months). Student t-test and Chi-Square statistics will be used to assess the absolute and percent weight change outcomes, respectively. We will also use descriptive statistics to identify the proportion of total participants achieving $\geq 5\%$ weight loss and the proportion achieving ≥ 150 minutes. Similarly, Student t-tests will also be used to assess pre to post intervention changes in waist, glucose, lipid, and blood pressure measures. Because we know that medications will effect these outcomes we will conduct separate sub-group analyses for lipid endpoints to control for statin use, and for blood pressure endpoints to control for blood pressure medication use.

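### Hypothesis 2 sets mean month-4 targets (5% weight loss, 150 activity minutes a week), but no planned test or interval relates either mean to its target

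*Combined protocol and SAP*

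**What the plan says.** The month-4 question belongs to the phase before randomization. Section 2.3 introduces the assignment to arms with "Following implementation of the non-randomized GLB-12", so at month 4 there is one cohort and no comparison group.

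Section 1.2 gives Hypothesis 2 as "Participants will achieve 5% weight loss and 150 minutes of self reported physical activity per week", with matching improvements in waist, glucose, blood pressure and lipids, at month 4. Section 2.18 restates the two targets as averages over participants. The weight target is at least 5% "weight loss (the definition of acceptable weight outcome in prevention programs". The activity target is at least 150 "moderately vigorous physical activity minutes per week (the recommended level in prevention programs".

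The Hypothesis 2 analysis plan in section 2.18 names two weight variables over months 0 to 4, absolute change in kg and percent change, and then says: "Student t-test and Chi-Square statistics will be used to assess the absolute and percent weight change outcomes, respectively". It adds "We will also use descriptive statistics to identify the proportion of total participants achieving" each target. Student t-tests are listed for pre-post change in waist, glucose, lipids and blood pressure. Activity minutes are not on that list.

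Under Hypothesis 1, section 2.18 promises intervals: "Summary descriptive statistics will include mean, median, standard deviation and confidence intervals for continuous variables". The same sentence returns under the exploratory aim. The Hypothesis 2 plan has no such sentence.

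**The concern.** A hypothesis that a mean reaches a stated target calls for an estimate of that mean, with its uncertainty, set against the target. The named analyses do something else:

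- **Percent change.** A chi-square is assigned to a continuous variable in one group. It needs a category and a reference proportion, and the sentence gives neither.
- **Absolute change.** A pre-post t-test has no change as its natural null. It does not ask whether the loss reached 5%.
- **Activity minutes.** Only the proportion reaching 150 is described. The mean, which is what the hypothesis is about, has no inferential analysis.

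The risk is that a very small p-value against no change is read as support for the 5% target, and that the uncertainty around both mean targets goes unreported. Effectiveness at month 4 is half of Aim 1.

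**Working it through.** **Plan's own figures.** The documents give no sample size, power or precision figure for Hypothesis 2, so there is none to reproduce. The one usable input is the SD of weight change in the section 2.18 power paragraph, 10.5 lb, which is a 12-month figure. As a check on that SD, a two-sample t-test with 120 per arm has noncentrality 3.8 / (10.5 × √(2/120)) = 2.80 and power 0.800 for 3.8 lb; for 4.4 lb the power is 0.901. Both match the stated 80% and 90%.

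**Inputs for month 4**

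- SD 10.5 lb, assumed to apply at month 4.
- n = 320 (all enrolled) to 240 (the plan's 25% attrition, also a 12-month figure).
- Mean baseline weight 180 to 220 lb. The documents do not give it, so this is assumed.
- SD on the percent scale approximated by 10.5 / mean weight, that is 4.8 to 5.8 points.
- Two-sided 0.05, from section 2.18.

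**Step 1: what the no-change t-test can tell.** The smallest significant mean loss is t(0.975, n−1) × SD / √n.

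| n | threshold (lb) | at 180 lb | at 220 lb |
|---|---|---|---|
| 240 | 1.34 | 0.74% | 0.61% |
| 320 | 1.15 | 0.64% | 0.52% |

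A 5% loss is 9 lb at 180 lb and 11 lb at 220 lb. That is 9 / 1.335 = 6.7 to 11 / 1.155 = 9.5 times the threshold. If the true mean loss were only 2%, with an SD of 6 points and n = 240, the test would still be significant with power 0.999.

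**Step 2: what an interval would give.** The 95% half-width uses the same formula, so it is ±0.52 to ±0.74 points ignoring clustering. Section 2.6 says "The GLB-12 intervention will be administered in groups of approximately 15-20 participants", so outcomes may correlate within a group. With m = 15 to 20 per group, k = n/m groups and an assumed ICC of 0.01 to 0.05, the half-width is t(0.975, k−1) × SD / √n × √(1 + (m−1) × ICC):

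- smallest: n = 320, m = 15, ICC 0.01, 220 lb gives 0.59 points;
- largest: n = 240, m = 20, ICC 0.05, 180 lb gives 2.201 × 0.678 × 1.396 / 180 = 1.16 points.

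Either can be set directly against 5%.

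**Step 3: the chi-square if at least 5% is the intended category.** Suppose 40% reach it (assumed). Against an assumed reference of one-third, z = (0.400 − 0.333) / √(0.333 × 0.667 / n), giving p = 0.028 (n = 240) or 0.011 (n = 320), significantly above. Against an assumed one-half, p = 0.002 or 0.0003, significantly below. The missing reference decides the conclusion.

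**Step 4: a proportion does not settle a mean.** If minutes were lognormal with mean exactly 150, the share at or above 150 is 1 − Φ(s/2), with s = √ln(1 + CV²). For an assumed CV of 0.5 to 1.25 this is 41% down to 31%. The documents give no SD for minutes. With an assumed SD of 100 to 200, the half-width for the mean is ±11 to ±22 minutes (n = 320) or ±13 to ±25 (n = 240), ignoring clustering.

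**Step 5: unmeasured weights.** If completers average 5% and 25% of the cohort are unmeasured with zero loss (assumed), the cohort mean is 0.75 × 5 + 0.25 × 0 = 3.75%. That 1.25-point shift exceeds the widest half-width in Step 2.

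**The case against.** The strongest reply has four parts.

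**The category can be inferred.** Section 2.18 calls at least 5% the acceptable outcome, and the primary endpoint uses the same cut. This stands: a reader might infer that the chi-square is impossible to run, but the documents support only that it is under-specified. The category is inferable, though not certain, because the next sentence treats that proportion as descriptive. The reference proportion is absent in either case.

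**The observed mean answers an aim to document.** In an uncontrolled phase, a mean set beside 5%, with the proportions reaching each target, goes some way. This also stands. The gap is the unreported uncertainty, not the absence of any answer.

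**The Hypothesis 1 interval sentence may carry over, and the biostatistician may choose appropriate tests.** The sentence sits in another hypothesis's plan and is not tied to 5% or 150 minutes. Leaving tests to later judgement does not supply a reference proportion. If carry-over was intended, one sentence would settle it.

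**The mixed model covers the outcomes.** It compares the two randomized arms and does not relate the month-4 cohort means to their targets.

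The pre-post t-tests for waist, glucose, lipids and blood pressure are not in dispute. They suit a claim of improvement.

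**Conclusion.** The concern holds in limited form. Hypothesis 2 is about two means and their targets, and no test or interval in its plan connects them. The weight test that is fully specified becomes significant at roughly one-seventh to one-tenth of the target loss, so significance says almost nothing about 5%. The chi-square lacks a reference proportion, and mean activity minutes have no inferential analysis.

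The size rests on the 12-month SD and attrition applied at month 4, an assumed baseline weight and the percent-scale approximation. The conclusion does not depend on their exact values.

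Two stronger readings should be resisted. A reader might infer that Aim 1 cannot be answered at all; the observed mean and the planned proportions answer it in part. A reader might also infer that the trial's main result is at risk; the primary endpoint is the randomized 12-month comparison, which this does not touch. It is a lower-priority correction.

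**What to change.** Replace the sentence that assigns the t-test and chi-square with:

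> Mean percent weight change (0–4 months) and mean weekly minutes of moderately vigorous physical activity at month 4 (from the pre-specified study instrument) will be reported with two-sided 95% CIs, allowing for GLB-12 group, and compared with 5% and 150 minutes. Absolute weight change (kg) will be reported with a paired t-test as supportive.

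In addition:

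- **Chi-square.** Drop it, or define it on the at-least-5% category against a stated reference proportion. The choice is the investigators'.
- **Activity source.** Name the instrument and keep the intensity limit. Section 2.17 lists both CHAMPS and past-month activity questions, section 2.6 also has activity diaries, and the plan does not say which yields the 150 minutes.
- **Proportions.** Report both with exact 95% CIs and all enrolled participants as the denominator, so that an unmeasured participant counts as not reaching the target. For scale, 50% of 320 gives 44.4% to 55.6%. The exact interval does not allow for clustering, and the report should say so.
- **Missing weights.** Add a sensitivity analysis for unmeasured month-4 weights, for example no change from baseline.

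Any formal decision rule (point estimate or lower limit) is for the investigators to set. The cost is SAP wording, with no new data. The downside is that a mean near its target may have to be reported as uncertain: for weight, within about 0.5 to 0.7 points of 5%, or up to about 1.2 points once clustering is allowed for under the assumed ICC.

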All analyses will be conducted in consultation with [name], the study biostatistician. Descriptive analyses and graphic displays will be used to identify outliers, missing data and patterns of attrition that will guide decisions about the use of transformations and appropriate tests. Demographic variables and baseline measures will be compared between the GLB+10TC and GLB+NC conditions. In all outcome analyses we will use an intent-to-treat (ITT) approach in which participants remain in the study arm to which they are randomized regardless of attrition. The primary analytic strategy will be a mixed models approach in which treatment group, time, and time by group interaction are treated as fixed effects, and subject and percent weight loss during the first phase of intervention (<3.5% and >3.5%) are treated as a random effects to account for individual subject variability. Hypothesis tests will be two-sided and significance will be set at the 0.05 level. Analytical tools will include SAS (SAS Institute, Inc., Cary NC), Stata (StatCorp LP, College Station, TX) and StatXact (Cytel, Inc. Cambridge, MA). Mixed models are applicable to longitudinal datasets that contain missing observations, with

the assumption that the data are considered to be missing at random (MAR) or ignorable missing. Although we will be proactive in maximizing subject retention, we anticipate 75% adherence over the 12-month intervention period. Those who drop out or are lost to follow-up will be compared to those who have completed intervention sessions and research assessments using standard parametric and non-parametric methods, as appropriate. We will examine the patterns of missingness and, if necessary, account for missingness in outcome analysis (e.g., the covariate approach). Finally, regression modeling will be conducted to adjust for covariates, including demographic variables such as age, race, sex, number of sessions completed, as well as any other variables that have been found to differ across treatment conditions at baseline.

Research Questions

Hypothesis 1 (feasibility): On average, we will enroll ≥ 107 participants per year for each of three years to GLB-12; they will complete $> 65\%$ of sessions, return $\geq 50\%$ of self-monitoring records and report above average program satisfaction at the 4-month assessment.

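### The Hypothesis 2 t-tests and the intervals for continuous Hypothesis 1 summaries ignore GLB-12 group membership, so their standard errors are too small if outcomes correlate within groups

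*Combined protocol and SAP*

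**What the plan says.** **Delivery.** Section 2.6 (Training and Supervision) states: "The GLB-12 intervention will be administered in groups of approximately 15-20 participants", "by three part-time lifestyle coaches". It adds: "Each coach will conduct 3-10 groups (GLB-12) per year and be responsible for all associated follow up protocols". Section 1.2 sets the sample: "Participants will be 320 non-diabetic adults, aged 65-80". Section 2.18 gives the enrolment target as at least 107 "participants per year for each of three years to GLB-12".

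**Hypothesis 2 analysis (section 2.18).** For weight: "Student t-test and Chi-Square statistics will be used to assess the absolute and percent weight change outcomes, respectively". For the other measures: "Student t-tests will also be used to assess pre to post intervention changes in waist, glucose, lipid, and blood pressure measures". The percentages reaching 5% weight loss and 150 activity minutes are to be described.

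**Hypothesis 1 analysis (section 2.18).** The approach is descriptive: "Summary descriptive statistics will include mean, median, standard deviation and confidence intervals for continuous variables and proportions, ranges and percentiles for categorical variables". The percentages with acceptable attendance and acceptable diary return are listed without an interval or test.

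**Clustering.** Neither Aim 1 analysis mentions GLB-12 group or coach. The mixed model at the start of section 2.18 has random effects for subject and for the phase-1 weight-loss stratum only. The Hypothesis 3 plan applies it to the comparison of arms; nothing applies it to Aim 1.

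**The concern.** Members of a GLB-12 group share a coach, a location, a season and weekly discussion. Their attendance and month-4 changes may therefore be more alike than those of people in different groups. An ordinary t-test or interval takes its standard error from the spread between individuals divided by the square root of their number. With positive within-group correlation, that understates the error of the mean.

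The month-4 analysis has one arm. The between-group variation goes straight into the error of the mean, with no second arm to share it. The program is meant for dissemination (sections 1.3 and 1.4), that is, to new groups, so this variation belongs in the stated uncertainty.

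At stake are p-values that are too small for modest changes in waist, glucose, lipids and blood pressure, and overstated precision for mean weight change around the 5% target and for continuous feasibility summaries.

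**Working it through.** **The plan's own figure.** None exists for Aim 1: the power statements in section 2.18 concern the two-arm 12-month comparison. Their standard deviations (SDs) serve below only as illustration. They do reproduce: with 120 per arm, a difference of 3.8 lb with SD 10.5 gives 80.0% power, and 4.3 mg/dl with SD 11.9 gives 79.9% (normal approximation).

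**Inputs from the documents.** N = 320; group size m = 15-20; 3 coaches; 3-10 groups per coach per year; 3 years; two-sided alpha 0.05.

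**Assumed input.** ICC by GLB-12 group of 0.01-0.05. The documents give no value.

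**Number of groups, two routes.**
- From group size: 320/20 = 16 to 320/15 = 21.3.
- From coach workload: 3 × 3 × 3 = 27 to 3 × 10 × 3 = 90, so mean sizes of 320/27 = 11.9 down to 320/90 = 3.6.

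The routes disagree. Even the minimum of 27 groups, at 15 each, would need 405 people.

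**Formulas.** Design effect DE = 1 + (m − 1) × ICC. Standard error multiplier = √DE. Effective N = 320/DE. Actual alpha = 2 × [1 − Φ(1.96/√DE)].

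| Basis | m | ICC | DE | SE multiplier | Effective N | Actual alpha |
|---|---|---|---|---|---|---|
| Group size | 15 | 0.01 | 1.14 | 1.07 | 281 | 6.6% |
| Group size | 20 | 0.01 | 1.19 | 1.09 | 269 | 7.2% |
| Group size | 15 | 0.05 | 1.70 | 1.30 | 188 | 13.3% |
| Group size | 20 | 0.05 | 1.95 | 1.40 | 164 | 16.0% |
| Workload, 90 groups | 3.6 | 0.01 | 1.03 | 1.01 | 312 | 5.3% |
| Workload, 27 groups | 11.9 | 0.01 | 1.11 | 1.05 | 289 | 6.3% |
| Workload, 90 groups | 3.6 | 0.05 | 1.13 | 1.06 | 284 | 6.5% |
| Workload, 27 groups | 11.9 | 0.05 | 1.54 | 1.24 | 207 | 11.5% |

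The nominal 95% interval covers 100% minus the last column: about 93% to 84% for groups of 15-20.

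**Degrees of freedom.** With 16-21 groups, t on 15-20 df is 2.13-2.09, against 1.97 on 319. Including this, a correct interval is wider by a factor of 1.13 (m = 15, ICC 0.01) to 1.51 (m = 20, ICC 0.05).

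**In outcome units (12-month SDs borrowed, N = 320, before the df correction).**
- Weight: half-width 1.97 × 10.5/√320 = 1.15 lb. It becomes 1.23 lb (m = 15, ICC 0.01) or 1.61 lb (m = 20, ICC 0.05).
- Glucose: 1.97 × 11.9/√320 = 1.31 mg/dl. It becomes 1.40 or 1.83 mg/dl.

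A half-width is also the smallest mean change that reaches significance against zero. A 5% loss would fall below 1.61 lb only if mean body weight were under 1.61/0.05 = 32 lb, so it stays significant.

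**Coach.** At 320/3 = 107 people per coach, an assumed coach ICC of 0.01 gives DE = 1 + 105.7 × 0.01 = 2.06. Three coaches cannot support an estimate of that variance.

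**The case against.** **Scope.** A reader might infer that every Aim 1 interval is too narrow. The documents do not support that. Section 2.18 lists intervals only for continuous variables. The attendance and diary-return percentages have no planned interval or test, enrolment is a count, and Hypothesis 2 names tests rather than intervals. This limit stands, and the point is confined accordingly.

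**Size.** The ICC is assumed, and nothing supports one value for attendance, weight, glucose, lipids and blood pressure alike. On the workload route the low end is nearly nil (DE 1.03). Both stand; they make the size uncertain but leave the direction unchanged for any positive ICC.

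**Importance.** The primary endpoint is the 12-month comparison of arms, no stated precision for Aim 1 is overturned, and only changes inside a narrow band would switch conclusion. The lack of a comparator is a larger limit on Aim 1, and wider intervals do not cure it. All of this is fair. Still, Hypothesis 2 is formally tested on several outcomes at the 0.05 level, and small risk-factor changes are where that band lies.

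**Flexibility.** Section 2.18 lets exploratory work guide the choice of tests, in consultation with a biostatistician. That leaves room for a correction, but clustering is not named, so it is only a partial answer.

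**Conclusion.** The point holds for the Hypothesis 2 pre-to-post t-tests (weight, waist, glucose, lipids, blood pressure) and for intervals on continuous Hypothesis 1 summaries such as sessions completed. As written, both understate the standard error whenever the ICC by group is positive.

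With groups of 15-20 and an assumed ICC of 0.01-0.05, standard errors should be 1.07-1.40 times larger and a nominal 5% test rejects about 7-16% of the time when there is no change. If the workload statement held instead, the design effect would be 1.03-1.54 and the rejection rate about 5-11%. The calculation takes equal group sizes and all 320 participants; fewer month-4 records would change the ratio little.

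A reader might go further and conclude that the month-4 weight loss claim is unsafe. It is not: a mean loss near 5% would remain clearly different from zero. Nor does this calculation bear on the 12-month primary endpoint, because randomization comes after GLB-12 and members of one GLB-12 group can enter either arm.

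**What to change.** In section 2.18, under the Hypothesis 1 and 2 analysis plans:

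- Estimate each participant-average month-4 change, and each continuous Hypothesis 1 mean, with a random intercept for GLB-12 group. Alternatively, use cluster-robust errors with a small-sample correction and df of about the number of groups minus 1. Avoid unweighted group means: with unequal group sizes they no longer estimate the participant average that Hypothesis 2 refers to.
- Use the same approach for any interval or test reported for a proportion, including the chi-square analysis of percent weight change.
- Report the ICC for each outcome. Show results by coach descriptively only.
- In section 2.6, reconcile the group size with the number of groups per coach per year.

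The cost is a group ID in the dataset, a few lines of SAP text and somewhat wider intervals. No extra participants or visits are needed.

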Demographic Questionnaire: will be used to collect data on sex, age, race, ethnicity, education, income and family contact information.

Weight and Height: will be taken twice using a standardized protocol. Weight will be measured to the nearest 0.1 kg at all screening/ assessment points using a digital scale (SECA 880) placed on a hard, flat surface. Height will be measured at screening events and the baseline visit only in street clothes, without shoes, using a portable stadiometer (Shorr productions) and rounded to the nearest 0.1 cm.

BMI: will be calculated as average weight divided by average height squared (kg/m²).

Waist Circumference: will be measured as an index of truncal fat using a standardized protocol. A Gulick tape will be placed around the bare abdomen horizontally at the midpoint between the highest point of the iliac crest and the lowest part of the costal margin in the mid-axillary line. Measurements are taken three times and averaged.

Fasting Glucose and Lipids (total, HDL and LDL cholesterol, and triglycerides): will be collected via finger stick after at least an 8 hour fast (last food/drink consumption will be documented prior to collection of sample). We will use the Cholestech LDX® System, with results available immediately, and adhere to all quality control measures published by the Cholestech Company.

Blood Pressure: will be measured using an automatic inflatable digital blood pressure monitor (OMRON HEM90HXC®) with appropriate cuff size according to a standardized protocol.

Nutrition/Nutrition Related Behavior: We will administer 2 questions from the CDC NHANES

Food Frequency Questionnaire and 14 items from the Mediterranean Diet Assessment Tool.

Physical Activity Behavior: We will administer, by interview, the Champs Physical Activity Questionnaire for Older Adults (46). This survey consists of 41 items that have been shown to be a highly reliable and valid measure of the weekly frequency and duration of various physical activities typically undertaken by older adults. It has been shown to be sensitive to changes following activity interventions in persons aged 65-90. We will also ask some questions by interview about past month activity level.

Other behavioral, psychosocial functioning and mood questionnaires and surveys are as follows:

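### Hypothesis 2 judges physical activity only by its month-4 level, not by change from baseline, so this component can look met with no increase in activity, or unmet despite a large one

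*Combined protocol and SAP*

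**What the plan says.** Hypothesis 2 is the effectiveness hypothesis for the 12-session group phase (GLB-12). Section 1.2 sets two numeric targets at month 4: "Participants will achieve 5% weight loss and 150 minutes of self reported physical activity per week". Section 2.18 repeats them as averages and specifies the activity as "self reported moderately vigorous physical activity minutes per week".

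The Hypothesis 2 analysis plan in section 2.18 then treats the outcomes differently:

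- **Weight:** "we will examine both absolute weight change (kg) and percent weight change pre to post-intervention (0-4 months").
- **Cardio-metabolic outcomes:** "Student t-tests will also be used to assess pre to post intervention changes in waist, glucose, lipid, and blood pressure measures".
- **Activity:** only a descriptive summary, "and the proportion achieving ≥ 150 minutes". No baseline comparison, change score or test is named.

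On design, section 2.3 says "Following implementation of the non-randomized GLB-12, participants will be assigned by a stratified block randomization scheme", so everyone receives GLB-12 and month 4 has no control group. The same section says "Major outcome assessments will be conducted at 0, 4, 12 and 24 months". Section 2.17 lists activity among the main outcome variables: "We will administer, by interview, the Champs Physical Activity Questionnaire for Older Adults". It describes that questionnaire as responsive to activity interventions in older people. It also mentions separate past-month activity questions.

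**The concern.** A level at month 4 cannot show that activity rose. With no control group, the participant's own baseline is the only comparator available at that visit, and the activity analysis does not use it. Sections 3.13 and 3.14 put no ceiling on activity at entry, so people already doing 150 minutes a week can enrol and count as achieving the target. Section 2.6 describes the programme goal as building activity up to 150 minutes, which is a statement about change.

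At stake is how one component of Hypothesis 2 is interpreted. A favourable figure may reflect who enrolled. An unfavourable one may hide a real increase from a low start.

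**Working it through.** **Is there a figure to reproduce?** No. The documents give no power, sample size or baseline value for activity, so the main check is textual.

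**Step 1. Outcomes side by side (section 2.18, Hypothesis 2).**

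| Component | 0-4 month change analysed? |
|---|---|
| Weight (kg and percent) | Yes |
| Waist, glucose, lipids, blood pressure | Yes, pre-to-post t-tests |
| Activity | No, proportion at or above 150 minutes only |

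**Step 2. Does another analysis fill the gap?** The repeated-measures mixed model under Hypothesis 3 compares the two randomised arms, with planned contrasts at 12 and 24 months. Hypothesis 3 does not name activity. Even if the model is extended to activity, a between-arm contrast does not estimate the gain over the shared first four months.

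**Step 3. What the planned proportion can hide.** Gain = month-4 proportion minus month-0 proportion. All proportions here are assumed.

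- 55 − 20 = 35 points
- 55 − 35 = 20 points
- 55 − 50 = 5 points

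The plan reports 55% in all three cases. If nothing changes, the expected month-4 proportion equals the baseline proportion. With the planned 320 enrolled (section 1.2), an assumed baseline share of 20%, 40% or 60% gives 64, 128 or 192 people counted as reaching 150 with no increase.

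**Step 4. What the mean target can hide.** Take a skewed (lognormal) baseline, with parameters assumed. Mean = median × exp(s²/2), and the share at or above 150 = 1 − Φ((ln 150 − ln median)/s).

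- Median 120, s = 0.8: mean = 120 × exp(0.32) ≈ 165 minutes, and the share is about 39%. The mean target is met at baseline.
- Median 60, s = 1.0: mean = 60 × exp(0.5) ≈ 99 minutes, and the share is about 18%. Here 150 − 99 = 51, so any mean rise short of 51 minutes, about half the baseline mean (51/99 = 0.52), counts as a miss.

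**Step 5. Is a change analysis feasible at the planned size?** For a paired comparison at two-sided alpha 0.05 (section 2.18) and 80% power, the detectable mean change = (1.960 + 0.842) × SD of change / √n.

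- n = 320: 2.802/17.889 = 0.157 SD
- n = 240: 2.802/15.492 = 0.181 SD. This is 320 × 0.75, borrowing the plan's 25% attrition figure for 12 months.

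The SD of change is not given. For assumed values of 100, 150 and 200 minutes a week, the detectable change is 15.7, 23.5 and 31.3 minutes (n = 320) or 18.1, 27.1 and 36.2 minutes (n = 240).

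**The case against.** The strongest defence is that 150 minutes is a legitimate attainment target. Section 2.18 calls it the recommended level in prevention programmes, and missing it after a large rise is a feature of any such target. The activity result is also descriptive: no test or power calculation depends on it. Both points are fair. They support keeping the proportion and limit the weight of this point. They do not explain why the month-0 proportion is not set beside it.

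Three stronger readings are tempting, and the documents do not support them.

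- *Baseline activity is collected and then ignored.* Section 2.18 compares baseline measures between arms and applies the mixed model to each of the other outcome measures. Activity is a listed outcome, so its baseline plausibly enters both. What is missing is the 0-4 month analysis.
- *Active enrollees could make the whole programme look effective.* Hypothesis 2 also requires weight loss and cardio-metabolic improvement, and these are judged by change. Only the activity component is exposed.
- *The activity definitions contradict each other.* Section 1.2 omits intensity, section 2.18 says moderately vigorous, and section 2.6 describes moderate intensity like a brisk walk. This is mostly shorthand. The narrower point stands: with a 41-item questionnaire, past-month questions and weekly diaries all available, section 2.18 does not name the source of the 150 minutes.

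A further objection is that a pre-post change without controls cannot attribute a rise to the programme. That is correct. Section 2.6 places baseline assessments mainly in January to March, so month 4 falls around May to July, and season alone could raise reported activity. A change analysis shows whether activity rose, not why.

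Finally, that the month-0 activity data exist is inferred from the assessment schedule and the outcome list. It is a reasonable inference, but the study flow chart could not be read to confirm it.

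**Conclusion.** The point holds for the activity component of Hypothesis 2. As written, the plan cannot show that activity increased between months 0 and 4, although it analyses weight and the cardio-metabolic measures that way. The omission is clear from the text. Its consequence is only possible, because baseline activity is not given: the hidden gain runs from 5 to 35 points across the assumed baselines, and the mean target may or may not already be met at entry. The randomised primary endpoint, the proportion with at least 5% weight loss at 12 months, is unaffected. The change is worth making because it is cheap and feasible at the planned size.

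**What to change.** In the Hypothesis 2 plan of section 2.18:

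1. Keep the month-4 proportion at or above 150 minutes, but report it beside the month-0 proportion in the same people. Give the share moving from below to at or above 150 and the share moving the other way, with a paired comparison such as McNemar's test.
2. Add the within-person change in minutes from month 0 to month 4 with a 95% CI, using a rank-based or transformed analysis if the minutes are skewed.
3. Name one questionnaire as the source and use the same moderate-or-higher items at both times. Align the wording in section 1.2.
4. State that this is an uncontrolled pre-post change, open to seasonal and self-report effects.

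The cost is one extra paired analysis on data that the assessment schedule indicates will be collected anyway. The activity result may look less favourable than the month-4 proportion alone.
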